15.5.2. Qualitative analyses

Aim 3. Explore the relationships among barriers to, facilitators of, and uptake of COVID-19 testing and COVID-19 vaccination. Coding and analytic methods of qualitative data from in-depth interviews will employ a directed content analysis approach¹⁴¹. Analyses will be carried out in the Dedoose platform and will begin with pre-determined codes based on the conceptual model (i.e., a “start list”), which will be expanded based on emergent findings. This start list fosters data integration across qualitative and quantitative data sets, because the same core constructs are assessed in each method. The primary

qualitative data analyst will lead the process of organizing codes into themes, in collaboration with an “interpretive community”¹⁴² made up of research team members at NYU (including study Co-Investigators and the Senior Advisors, Drs. [name] and [name]) and NMIC. We will attend to trustworthiness and rigor in analysis using an audit trail and with member checking with the CAB and study participants. Integration of qualitative/quantitative results will use the joint display method²⁶. A joint display is a state-of-the-art visual tool (i.e., a side-by-side visual presentation of results) to integrate data sources. [name] will lead the effort to integrate data with the interpretive community. This will be an iterative process in which each joint display table reveals insights about the merged findings that shape subsequent iterations. Thus, joint displays are both a method and a cognitive framework for data integration and facilitate the production of new inferences²⁶. We are experienced with mixed methods data integration and joint display methods^{36,92-93,96,143}.

15.5.3. Data integration

Integration of qualitative and quantitative results will follow procedures outlined by Fetter and colleagues (2013) and use the joint display method¹⁸². A joint display is a state-of-the-art visual tool (i.e., a side-by-side visual presentation of results) to integrate data sources. The process brings about new insights beyond the information gained from the separate quantitative and qualitative results. Drs. [name] will lead the effort to integrate data with the interpretive community (including CAB). This will be an iterative process in which each joint display table reveals insights about the merged findings that shape subsequent iterations. Thus, joint displays are both a method and a cognitive framework for data integration and facilitate the production of new inferences¹⁸². We are experienced with data integration and joint display methods¹⁸³⁻¹⁸⁵.

All data provided to the CAB will be de-identified.

16. Safety Management & Study Administration

16.1. Data collection and management

16.1.1. REDCap

REDCap (Research Electronic Data Capture) will be used through all study phases. REDCap is a secure web-based application for building and managing online surveys and databases. Data can be entered from anywhere in the world over a secure web connection with authentication and data logging. It allows for multi-site access; that is, REDCap databases/surveys can be used by researchers from multiple sites and institutions. It includes features such as a built-in project calendar, a scheduling module, and reporting tools. REDCap can be installed in a variety of environments for compliance with such standards as HIPAA, 21 CFR Part 11, FISMA (low, moderate, high), and international standards. Only trained study staff will have access to the REDCap database. We have developed a comprehensive REDCap database for two ongoing studies and can adapt this database architecture for the proposed study. Thus private, identifiable information will be collected, but will be kept confidential.

16.1.2. Protection of confidentiality in REDCap

Participants will be identified by their Participant Identification Number in the REDCap database. A separate form linking participants’ names with the Participant Identification Number will also be included in REDCap. All consent forms will be signed in REDCap (the eConsent feature) and all assessments will be conducted in REDCap. Documentary evidence of COVID tests results will also be entered into REDCap. REDCap was designed specifically to protect patient and research participant

privacy and confidentiality while assisting investigators in conducting clinical research. The REDCap database can be shared among NYU authorized staff.

We will use computer-assisted personal interviewing (CAPI) and audio computer-assisted self-interviewing (ACASI) for sensitive sections of the assessments. In ACASI the respondent listens to digitally recorded questions and response categories through headphones, and enters her/his answers by using the computer keyboard or touching the computer screen. We have used ACASI with participants in past studies and found that participants were comfortable with using computers and appreciated the privacy it afforded. At each assessment period, the participant can opt out of the entire assessment or any part of the assessment.

Audio-recordings and transcripts will be stored on NYU's cloud-based and password-protected application, NYU Box. Recordings will be professionally transcribed within six months of collection and audio-recordings will be deleted within six months of transcription. Transcriptions will not include identifying information and are labeled with the participant's identification number.

Participant safety will be monitored by query regarding adverse events at all contacts and social harms in domains such as occupation, health care, and housing will be assessed at FU assessments.

16.1.3. Locator form

We are leaders in the development of successful tracking and retention strategies. Minimal contact information will be collected during the screening process. At the time of enrollment, after providing signed informed consent, the participant will complete a detailed locator form, which is stored in the REDCap database. The project staff member will solicit the names and contact information of at least three individuals who will know how to reach the participant in the future. Participants may provide the names of case managers and other professionals, as well as personal contacts. A locator form is a crucial component of the retention strategy. We will obtain email addresses, cell phone numbers, Facebook IDs, and other social media IDs, if participants are comfortable being contacted at these virtual locations. The project will maintain an open Facebook page to facilitate communication. The locator form is updated with participants at regular intervals. Participants are instructed to get in touch with the study if contact information changes. Staff will reach out to update locator information in between follow-up periods.

16.1.4. Retention plan

We will use a detailed locator form that is updated regularly, maintain regular contact with participants, ensure adequate, prompt, fair, and timely compensation with Clincard¹⁹⁰ (funds are available to participants almost immediately), implement specific technical tracking strategies, and train all staff on retention strategies¹⁹¹. For the participant, contact info will include cell phone number, email address, physical address, and social media handles, as well as contact information for at least three individuals who will know how to reach the participant. Attrition is highest in the early phases of studies, and regular contact during this period fosters retention¹⁹². Thus, participants will be contacted within one month to update locator information. Participants will receive compensation if they contact the study to update contact information. (Compensation amounts are provided below.) We will send birthday and holiday cards to build rapport, and returned mail will help identify participants at risk of attriting. Tracking includes direct contact tracking and network-based tracking. This begins with text and social media messages, phone calls, and letters to the participant and individuals on the locator form; repeated attempts will be made as necessary. If place-based tracking methods are unsuccessful, we will initiate systems-level tracking (e.g., searching web-based directories). We will create a positive project

ethos to increase engagement (communicating respect, no judgement, confidentiality, autonomy/choices) and tap into altruism¹⁹¹. We estimate $\geq 80\%$ of assessments will be completed.

16.1.5. Data sources for optimization trial

- Consent forms – screening, enrollment
- Locator form
- Structured assessment batteries: screening, BL, FU
- Brief assessment of peers as part of Component C
- COVID testing form (date, location/type of test, test result, type of confirmation, etc)
- COVID vaccination form (date or dates of vaccination doses, type of vaccine)
- Intervention component manuals
- Qualitative interview guide

16.2. Confidentiality

All data and records generated during this study will be kept confidential in accordance with Institutional policies on subject privacy. The Investigator and other site personnel will not use such data and records for any purpose other than conducting the study.

The safeguards to maintain subject confidentiality are described in the section on Data Collection and Management.

Eligible participants are told about the longitudinal component of the study as part of the enrollment informed consent procedure, and the consent form states that we will try to contact them in the future and how we will do so. We inform participants that we will not disclose anything about them as part of the tracking process other than that they are a participant in a “community health project.” We will use a generic name for the study that does not disclose anything about the participant.

16.3. Data sharing with RADx-Up

The study will obtain permission from participants to collect and share de-identified data with the NIH RADx -UP Coordination and Data Collection Center (CDCC) and RADx Data Hub using specific language in the Informed Consent Forms (ICF).

16.4. Regulatory and ethical considerations - Data and safety monitoring plan (DSMP)

16.4.1. Data safeguards

The project will maintain study offices in a field site maintained by the NYU Silver School of Social Work located in lower Manhattan. Access to NYU offices is restricted to research staff. The NYU Silver field site building is secure and monitored by security staff.

The secure and password-protected REDCap database is used for study activities. Consent forms will be signed (as appropriate) and structured assessments will be conducted in REDCap. REDCap was designed specifically to protect patient and research participant privacy and confidentiality while assisting investigators in conducting clinical research. System-level and application-level security features include SSL encryption of internet traffic (e.g., https pages), hosting in a secure data center with nightly backup, fine-grained control over user privileges, detailed audit trails, record-locking, and de-identification functions for data export. Participants will be identified by their Participant Identification Number (PIN) in REDCap forms and assessments. Only research study staff have access to the REDCap database.

All computerized data that are not in REDCap (transcripts of qualitative interviews, audio-recordings) are kept on computers that are double password-protected and are only labeled with PINs. Audio files are transferred to a secure cloud-based storage system daily (NYU Box), which is also double password protected and available only to project staff. Audio-recordings are deleted within six months of their creation date.

16.4.2. Confidentiality safeguards

All participants receive a participant identification number (PIN). This number will be used for all materials, audio-recordings, transcripts, study visit notes, and assessments. No other information that would disclose the participant's identity will be found on any assessments, notes, audio files, or in the transcripts of qualitative interviews.

Study staff do not collect paper forms; all materials are located in the secure REDCap database. Participants provide signed consent electronically and the signature is recoded in REDCap. Staff receives training about confidentiality. Participants will be provided a paper copy of the consent form that includes contact information for the research team PI and the IRB as appropriate. Participants can use this contact information to report adverse events or unanticipated problems.

Names and other identifying information will be redacted from transcripts.

16.4.3. Ethics training

All research personnel will have completed Collaborative Institutional Training Initiative (CITI) training or an equivalent training before the research begins.

16.4.4. Certificate of Confidentiality

Participants will be informed that the study will obtain a Certificate of Confidentiality from the awarding institute at the NIH to support protection of their data. All data will be used strictly for research purposes.

16.5. Collection and reporting of “Reportable Events”

Several mechanisms will be put in place to monitor potentially adverse events that participants may experience while enrolled in the study, whether they are related to project participation or not. These events are classified as either Reportable, Adverse, or Not Harmful/Expectable, as described below, and will be reported to the IRB and Program Official at the study's awarding institute (i.e., the Sponsor) accordingly, as described below.

In accordance with federal regulations governing Institutional Review Boards (45 CFR 46 and 21 CFR 50 and 56) and Guidance on Reportable Events from the Office of Human Research Protection, the Food and Drug Administration, and NYU, the IRB will review only unanticipated problems involving risks to participants or others. An unanticipated problem means that the incident, experience, or outcome is not expected (in terms of nature, severity, or frequency) given the research procedures that are described in the protocol-related documents, such as the IRB-approved research protocol and informed consent documents; and the characteristics of the subject population being studied.

While there are many terms used by behavioral/social, clinical, and biomedical scientists to define a given type of reportable event (e.g., serious adverse event [SAE], adverse event [AE], adverse

experience, etc.), the IRB uses the following single definition for an immediate, single-incident IRB-reportable event: A Reportable Event is an unanticipated problem involving risks to participants or others (“Unanticipated Problem”) and any event or information that (1) was unforeseen and (2) indicates that the research procedures caused harm to participants or others or indicates that participants or others are at increased risk of harm. (Other types of adverse events will be reported in aggregate or summary form to the IRB and Sponsor, as we describe below.)

The following definitions are used by IRB at NYU:

Unanticipated - An event is unanticipated when its specificity or severity is not consistent with, and not included in, the current investigator brochure, protocol, consent form, package insert or label; or unanticipated in its frequency, severity, or specificity.

Related - An event is related to research procedures if in the opinion of the Principal Investigator, it was more likely than not to be caused by the research procedures or if it is more likely that not that the event affects the rights and welfare of current participants.

Harmful - An event is harmful if it has caused harm to participants or others, or placed them at increased risk of harm. The harm does not have to be a direct harm to be reportable. The harm, as assessed by the Principal Investigator, may have created increased risk (e.g., losing a laptop with participant data such as an audio-recording). Additionally, the harm does not have to be harm to participants; it could involve risk to others (researchers, technicians, bystanders, the public, etc.).

Note: Non-medical events (e.g., breach of confidentiality, emotional breakdown, loss of insurance due to study participation, etc.), if unanticipated, would also be reportable to the IRB.

Thus, some examples of Reportable Events for the present study might be the following:

- Emotional breakdown requiring psychiatric intervention as a result of study participation
- Suicidal threat or behavior as a result of study participation; namely, the serious threat or attempt to inflict serious bodily harm to oneself that may result in death
- Serious violent threats or behaviors as a result of study participation including any threats, ideations or attempts to seriously injure or kill another person
- Experiences of domestic violence as a result of study participation
- Loss of employment or income as a result of study participation (participant was turned down for a new job, lost a job, or experienced other problems at work)
- Loss of education as a result of study participation (participant was turned down by an educational program, told to leave an educational program, or experienced other problems at school)
- Refused medical or dental care as a result of study participation
- Problems with health insurance as a result of study participation (participant lost health insurance, had a problem getting new health insurance, or experienced other problems related to health insurance)
- Problems with housing as a result of study participation (participant had trouble getting or keeping housing, or had other problems related to housing)
- Incarceration of an enrolled participant through the study period because the study is not approved to include prisoners. (The present study will not be approved to conduct research activities with participants while they are incarcerated, and any subjects incarcerated during the course of the study and unable to attend study visits will be withdrawn.)

- An unresolved participant complaint that indicates a potential increase or unexpected risk
- New information that presents a change to the risks or potential benefits
- A deviation or violation from the IRB approved protocol
- Unintentional direct or indirect violation of participant confidentiality by study staff.

Table 5: Summary of Events Classification and Actions Taken

Level of event	Examples	Action Taken
Reportable (unanticipated, related to study participation, harmful)	Hospitalizations at least overnight for any medical and/or psychiatric reason associated with study participation; suicidal or homicidal ideation related to study participation; incarceration of an enrolled participant through the study period; an unresolved participant complaint that indicates a potential increase in risk or unexpected risk; new information that presents a change to the risks or potential benefits; a deviation or violation from the IRB-approved protocol; unintentional direct or indirect violation of participant confidentiality by study staff.	(1) Report event to the IRB within 24 hours , (2) Report event to Sponsor's Program Official within 24 hours , (3) Report additional details of event and actions taken to the NYU IRB and NIH Program Official within 72 hours , (4) Respond to requests for additional information by and/or recommendations from the IRB and NIH.
Adverse but not "Reportable" (anticipated in the consent form or unanticipated, may or may not be associated with study participation, harmful)	Hospitalizations at least overnight for any medical and/or psychiatric reason not associated with study participation; suicidal or homicidal ideation not related to study participation; drug overdose, namely, an emergency room visit and/or hospitalization due to a reaction to non-prescribed medications not associated with study participation; life threatening or disabling/incapacitating events affecting health and well-being such as serious accidents or physical attacks that result in injury not related to study participation; death not related to study participation; serious distress as a result of study procedures.	1) Document event on internal Events Log Form including whether it appears to be related to study participation, (2) Report events in aggregate or summary form to IRB annually, (3) Report events in aggregate or summary form to Program Official at NIH at the time of the Progress Report, (4) Provide clinical referral as appropriate at the time of event.
Not Harmful/Expectable (largely anticipated, not harmful)	Mild to moderate distress or anxiety as a result of study procedures	Not reported to IRB or NIH but provide clinical referral as appropriate at the time of event.

16.5.1. Reporting of adverse events that are not "reportable events"

Adverse Events do not meet the criteria to be considered a Reportable Event, may be unanticipated or anticipated (that is, described in the protocol or consent form), may or may not be associated with study participation, and are harmful or potentially harmful to the health and well-being of participants and others.

Thus, events uncovered during the course of the study will be classified as Reportable, Adverse, or Not Harmful/Expectable. A description of these three types of events and the actions to be taken for each are presented in Table 5.

16.6. Assessing events

As means of assessing events, some of which may be Not Harmful/Expectable, Adverse, or Reportable, we will administer a Social Impact Form that prompts for events that could occur as a result of participation in a study. Social impact will be assessed using a structured interview at each FU assessment. This assessment will probe for social, psychological, physical, housing, and other problems that have occurred as a result of study participation.

Furthermore, participants will be reminded to report problems, whether related or potentially related to study participation or not, to study personnel between scheduled assessments. They will be instructed on how to contact study personnel should problems occur between visits. Event impact will be formally and informally monitored, formally documented, and steps will be taken to prevent future similar events from occurring.

When an event is reported, it will be documented on an internal Events Log Form. The Events Log Form will assess the details, seriousness, and outcome of the event. As noted in Table 5, events are categorized as Not Harmful/Expectable, Adverse, or Reportable. [name] will determine whether an event is Not Harmful/ Expectable, Adverse, or Reportable.

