Perceived susceptibility to, severity of COVID-19	Wong perceived susceptibility to (three items), and perceived severity of COVID-19 infection (three items) scales ¹⁰⁵
Perceived benefits of COVID-19 testing	Guidry 4-item Perceived Benefits of COVID testing ¹⁰⁶ ; $\alpha = 0.82$
Distrust and fear of COVID-19 testing	10-items assessed on a 5-point Likert-type scale drawn from existing reliable scales ¹⁰⁶⁻¹⁰⁸
Counter-narratives (conspiracy theories)	6-items assessed on a 5-point Likert-type scale drawn from existing reliable scales (e.g., I could be a guinea pig for a test with unknown consequences). ^{109,110}
Cognitive biases	Measurement of BE biases ⁴²
Behavioral Intentions	Various testing scenarios assessed with 3 items (e.g., I intend to get a COVID-19 test regularly) on a 6-item Likert scale ¹⁰⁶
Motivation/readiness	Importance of COVID testing and confidence in ability to get serial screening and tested as needed on a 1-100 scale. ¹¹¹
Social influences	
Perceived social norms	Adapting Latkin we will assess social norms using four items: injunctive (e.g., My co-workers encourage me to get a COVID test); descriptive (e.g., What percent of your co-workers do you think have gotten a COVID test) ¹¹² . $\alpha = 0.77$.
Altruism & collective responsibility	Three items on testing as an altruistic act (e.g., My getting tested helps my community reduce the spread of COVID) ¹⁰⁸
Structural influences	
Structural barriers to COVID-19 testing	Perceived barriers including poor access related to insufficient local sites, lack of paid sick leave, lack of childcare, language barriers ¹¹³
PRIMARY OUTCOME	
COVID-19 testing	COVID testing behavior (see protocol for definition)
SECONDARY OUTCOMES	
COVID-19 testing	Confirmatory and/or re-testing, contact tracing (by participant), self-isolation, health care, unintended consequences of testing
Vaccination	Testing behavior - CDE
	Vaccine Acceptance - CDE
	Attitudes toward COVID-19 vaccination ¹⁰⁶⁻¹⁰⁸ , receipt of vaccination doses
Intervention process domains	
Intervention acceptability	Client Satisfaction Questionnaire (YCSQ) –17 items; reliable and valid measure ¹¹⁴
Intervention social harms	Assessment of project-related social harms experienced in social and occupational domains.
Feasibility/Intervention dose	
Intervention dose	Number of assigned components attended, if assigned: number of peers educated, navigation contacts completed and their characteristics/content

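### The Social Impact Form is worded to elicit only problems that participants link to the study, which conflicts with the plan's intent to monitor events whether or not they are related

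*Combined protocol and SAP*

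**What the plan says.** - **The form.** Section 16.6 presents the Social Impact Form as a way of assessing events that may turn out to be Not Harmful/Expectable, Adverse or Reportable. It is a structured interview given at each follow-up. Its content is described in two ways: "we will administer a Social Impact Form that prompts for events that could occur as a result of participation in a study", and then "This assessment will probe for social, psychological, physical, housing, and other problems that have occurred as a result of study participation".
- **The assessment battery.** Table 4 (Section 14.1.1) lists, among the intervention process domains, "Assessment of project-related social harms experienced in social and occupational domains".
- **The stated intent.** Section 16.5 sets up mechanisms to "monitor potentially adverse events that participants may experience while enrolled in the study, whether they are related to project participation or not".
- **Who judges relatedness.** Section 16.5 counts an event as related if "in the opinion of the Principal Investigator, it was more likely than not to be caused by the research procedures", or if it more likely than not affects participants' rights and welfare. Section 16.7 has the researchers decide before an IRB report. Table 5 has staff record apparent relatedness on the Events Log Form.
- **Unrelated harms.** Table 5 and Section 16.5.1 define Adverse events as harmful events that may or may not be associated with participation. Section 16.8 provides for summary reporting of unrelated ones.
- **Other routes.** Section 16.1.2 says "Participant safety will be monitored by query regarding adverse events at all contacts" and that "social harms in domains such as occupation, health care, and housing will be assessed at FU assessments". Section 16.6 also has participants reminded to report problems between visits, related or not. Unintended consequences are a secondary outcome in Table 4 and in Sections 14.4 and 15.3.

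**The concern.** A form that asks for problems caused by the study requires the participant to make a causal judgement before anyone on the study team sees the event. A participant who does not make that link can truthfully answer no, and the investigator then has nothing from this form to classify.

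This matters here because the plausible social harms are indirect. Section 4.1.1 names losing work, losing housing and deportation among the fears attached to a positive result. Sections 14.1.4 and 14.3 state that the study does not itself test participants. Someone who tested because of a component and then lost shifts may reasonably blame the test, the illness or the employer rather than the study. Yet the Reportable Event examples in Section 16.5 include employment, income and housing problems that result from participation, so this is a chain the investigator needs to be able to examine.

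**Working it through.** No arithmetic applies: the plan states no harm rate or bound, and the point depends on none. The check sets the provisions side by side.

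1. **What the form should supply.** By Section 16.6 it helps identify events in all three classes, including Adverse. By Table 5 and Section 16.5.1, Adverse includes harms not associated with participation.
2. **What the form is said to elicit.** The Section 16.6 sentence quoted above restricts it to problems resulting from participation. Table 4 restricts the measure to project-related harms. As described, the form cannot elicit the unrelated part of a class that it is meant to feed.
3. **Consistency with intent.** Section 16.5 covers events regardless of relatedness. Section 16.1.2 states the follow-up assessment of social harms without an attribution limit. Section 16.6 and Table 4 add one, so the four places do not agree.
4. **Order of judgement.** Sections 16.5 and 16.7 give relatedness to the Principal Investigator and researchers. The form's wording puts a participant's attribution ahead of theirs for whatever enters by this route.
5. **A worked pathway.** A component prompts a test, the result is positive, the participant isolates and loses work. At the next follow-up the form asks about problems caused by the study, and the participant, who blames the illness, says no. The remaining routes are:
   - *Adverse-event query at all contacts (Section 16.1.2).* It carries no attribution limit, but no domains or wording are given. Whether a participant would raise a lost job in reply is uncertain.
   - *Social harms at follow-up (Section 16.1.2).* The domains fit. However, this appears to be the same measure that Section 16.6 and Table 4 define with the limit, and it is not shown to be a separate one.
   - *Between-visit reporting (Section 16.6).* It covers unrelated problems but depends on the participant coming forward.
   - *Unintended consequences.* Sections 14.4 and 15.3 list this under a positive result or diagnosis, so it fits this pathway. Table 4 states no such condition. No section says that the answers reach the Events Log or event classification.
6. **Result.** The event can be missed on the form and may be caught elsewhere. The one secondary outcome best placed to catch it has no stated link to safety review.

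**The case against.** The strongest reply is that the form itself is not in the documents. The sentence saying it prompts for events that could result from participation fits a checklist of event types with relatedness judged later, and the Adverse category points the same way. That is a fair reading. However, the more specific sentence that follows and the Table 4 entry both carry the attribution limit, and a form built from them would carry it too. The reply shows that the protocol text is ambiguous, not that it is sound.

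Other parts of the reply stand and limit the point. A reader might infer any of the following, and the documents support none of them:

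- **That participants decide causality.** Sections 16.5 to 16.7 and Table 5 leave it with the Principal Investigator and study staff. Participants at most pre-filter one route.
- **That this is the only structured harms instrument.** Table 4 also collects unintended consequences of testing, and lists common data elements on housing, employment, insurance and the effects of COVID. The documents do not say which of these elements are repeated at follow-up. The accurate statement is narrower: it is the only harms measure described as a structured interview across social, psychological, physical and housing domains at each follow-up.
- **That such harms never reach review.** The other routes may catch some.
- **That harms comparisons between component levels will be biased.** No such comparison is planned, and unequal attribution by component is conjecture.
- **That a bound on the true harm rate follows.** Any figure would need an assumed fraction of harms captured, for which the documents give no basis.

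The study is also classed as minimal risk (Section 16.11), which bears on priority.

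**Conclusion.** The point holds as a conflict of wording with a practical consequence. Section 16.6 and Table 4 restrict the follow-up harms interview to problems the participant links to the study. Section 16.5 intends monitoring regardless of relatedness, and Table 5 needs unrelated harms as well. If the form follows the stated wording, indirect harms can be missed there, and their capture depends on routes that have no stated wording, rely on the participant coming forward, or are not tied to event review.

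The size cannot be put as a number. In scope, it affects one form, given at the two follow-ups (weeks 6 and 12) to all participants assessed. The conclusion assumes that the form is built as Section 16.6 and Table 4 describe it, and that some participants would not link a test-related loss to the study. It touches safety ascertainment only and leaves the primary efficacy analysis unaffected. It merits a change mainly because the change is cheap, and confidence is medium because the form has not been seen.

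**What to change.** 1. In Section 16.6 and Table 4, describe the Social Impact Form as asking about any problem in its existing domains since the last interview. Section 13.4.3 already sets that recall period for the follow-ups.
2. For each problem endorsed, add one item asking whether the participant thinks it was connected to the study or to a COVID test.
3. State that the investigator then classifies relatedness under the Section 16.5 definition, with the participant's view recorded as information only.
4. State that unintended-consequences responses (Table 4, Sections 14.4 and 15.3) go to event review and, where they describe a harm, to the Events Log Form. Say also whether that item is asked of everyone or only after a positive result, since Table 4 and Sections 14.4 and 15.3 differ.

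The cost is one reworded REDCap form, one follow-up item per endorsed problem, a routing rule, and IRB approval under Section 16.10. The downside is more unrelated events to log and classify, for which Table 5 and Section 16.8 already provide a category and summary reporting. If the form in use already asks without attribution, only the protocol text and the routing rule need to change. If data have been collected under the restricted wording, keep the two periods distinguishable when events are tabulated.
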